Common Treatments for Common Colds: A Pilot Study

RESEARCH PROTOCOL

[**Squirting Nasal saline solution Or Routine Treatment (SNORT) Study**]

Investigators

[name], [name], [name], [name], [name]

Aims

This project aims to compare the effectiveness of the addition of nasal saline spray to routine care for minimisation of the symptoms of acute URTIs. It also aims to assess the feasibility of conducting a randomised controlled trial for this purpose in general practice and to refine the processes of the trial.

Synopsis

Over the last few years, the National Prescribing Service (NPS) (<http://www.nps.org.au/>) has conducted regular campaigns aimed at educating the public about appropriate treatments for the common cold. They have continually reinforced the message that common colds are caused by viruses, and therefore antibiotics are likely to have no benefit. The NPS have produced resources to educate the public that treatments such as nasal saline, steam inhalation and decongestants that relieve symptoms are more helpful than antibiotics for common colds and viral upper respiratory tract infections.

However, the effectiveness of isotonic nasal saline spray for relief of common cold or acute rhinosinusitis symptoms has not been adequately evaluated – most studies have been too small or of poor methodological quality. Therefore this pilot study aims to determine the feasibility of conducting a general practice based, randomised controlled trial to assess the efficacy of nasal saline spray on the duration of general unwellness and symptoms associated with the common cold or acute rhinosinusitis.

In this study, consenting patients who have visited their GP because of a common cold or acute rhinosinusitis will be randomised to either nasal saline spray plus usual care or usual care alone. All study participants will be requested to not use steam inhalations, or any nasal decongestants or nasal sprays other than the trial medication for the duration of their participation in this study. The duration of general unwellness, cough, runny or blocked nose and sore throat, as well as the use of other treatments including antibiotics will be compared in both groups. Patients will be followed up until their first day of wellbeing or for 6 weeks, whichever occurs first.

We will assess the willingness of general practice patients to participate in this study (recruitment rate), their ability to comply with the study protocol, withdrawal rate, and any practical issues that arise within the general practice during the recruitment phase. Additionally, we will assess the practicality of and any issues associated with the procedures for following up patients by the research officer.

Research question(s)

- In patients with common cold or acute rhinosinusitis, does application of an isotonic nasal saline spray at least four times per day decrease duration and severity of general unwellness associated with these conditions, compared with usual treatment (excluding any nasal decongestant agents and steam inhalations)?
- In patients with common cold or acute rhinosinusitis, does isotonic nasal saline spray decrease antibiotic use compared with usual treatment (excluding any nasal decongestant agents)?
- In patients with common cold or acute rhinosinusitis, does nasal saline spray decrease severity and duration of malaise, compared with usual care (excluding any nasal decongestive agents)?

P all patients 2 years or older with common cold or acute rhinosinusitis

I nasal saline 4 times per day + usual care (excluding any nasal decongestants)

C usual care (excluding any nasal decongestants)

O duration and severity of nasal stuffiness, cough and rhinorrhea

Secondary research questions:

- What is the feasibility of conducting this randomised controlled trial of isotonic nasal saline solution in general practice?
- What is the acceptability to patients of isotonic nasal saline spray in treatment of nasal stuffiness, cough and rhinorrhea?

Background & Literature review

Troublesome cough, nasal stuffiness and rhinorrhea (runny nose) are common symptoms associated with viral upper respiratory tract infections (URTIs). These symptoms may persist for many weeks, and contribute to a significant percentage of patient visits to GPs each year (estimated to be about 6% of general practice consultations¹. The diagnosis of post viral cough is highly variable, with poor agreement on the causation being labelled as bronchitis, post nasal drip or sinus problems. Antibiotics are commonly prescribed in this situation, particularly if the patient reports coloured mucus², yet the evidence suggests a limited and problematic role for antibiotics for post viral cough. The National Prescribing Service (NPS) has produced patient education resources promoting the benefit of treatments such as nasal saline, steam inhalation and decongestants over antibiotics for viral URTIs.

Nasal saline irrigation is a popular treatment for sinonasal conditions. Its potential mechanism for alleviating upper respiratory symptoms is by clearing excess mucous, reducing congestion and improving breathing.³ It is reported to increase the frequency of nasal ciliary beating, thereby improving mucociliary clearance.⁴ In addition to relieving sinonasal symptoms, nasal saline irrigation may also remove

infectious material from the sinuses and reduce cough associated with post-nasal drip.⁵

The research literature suggests a clinically significant benefit of nasal saline in the treatment of cough associated with chronic rhinosinusitis and established sinus infections, and for assisting mucociliary clearance.³ However, studies investigating the clinical benefit of nasal saline in acute URTIs are predominantly small and methodologically flawed, although they do suggest some benefit.⁶ No studies on the benefit of saline nasal spray when post viral cough was the presenting symptom were identified, and none that documented the reduction in antibiotic usage by the adoption of this treatment strategy.

This project explores these issues through an open label, randomised clinical trial which aims to compare the effectiveness of the addition of nasal saline spray to usual treatment. The duration of cough as well as the use of other treatments, including antibiotics, will be documented in both groups.

Methods

Research Design – randomised controlled open label trial.

Participant recruitment – Participating GPs will opportunistically identify potentially eligible patients as they present for a consultation for treatment of the common cold or acute rhinosinusitis, and initiate discussion to gauge interest and determine eligibility. Following this consultation, the Practice Nurse (or another suitable staff member) will continue discussions with potentially interested patients, answer their questions, and obtain informed consent.

Inclusion criteria

- Patient is aged 2+ years and has had symptoms of cold (runny nose, sore throat, sneezing, cough lethargy etc), or acute rhinosinusitis for at least 5 days and up to but not more than 3 weeks.

Exclusion criteria

Patients who:

- wish to use any treatment involving a volume of liquid going into the nose (e.g. steam inhalations, nasal sprays, nasal decongestant agents nasal douches, neti pot etc). Participants who have previously been using these may be included, provided they agree to discontinue use for the duration of their participation in the study

OR who have:

- known or suspected Chronic Obstructive Pulmonary Disease (COPD)
- suspected pertussis infection
- facial anatomical abnormalities
- cognitive impairment preventing informed consent
- physical impairment preventing compliance with the study protocol

Recruitment of participating GPs – there is a core group of GPs & associated general practices who have been involved in the development of this project – UQ Health Services ([name], [name], [name]), Inala Indigenous Health ([name]) and Inala Primary Care. It is expected that additional GPs will be recruited through the South East Queensland Research Network (a network of GPs who have participated in general practice based, clinical research) and the UQ General Practices of Research Excellence (GPs who have lead clinical research in their own practices).

Sample Size – 60 participants, 30 in each group.

Randomisation and allocation to study groups – patients will be randomised to either the intervention or control group. Randomising will be done at the Discipline of General Practice using computer generated random sequences in blocks of ten patients. A set of sealed, opaque, sequentially numbered study packs will be delivered to each participating general practice. Once a patient has consented to participate in the study, they will be allocated a study identifier, and will be given a study pack. The study pack will contain the first fortnight's patient diary, and sufficient study medication for a fortnight. Study packs for the control group will contain 3 packs of Vicks Vapor Drops or similar, of comparable size to the nasal saline spray. This will be a 'thank you' to control group participants and will ensure that all study packs look similar such that practice staff and patients remain blinded to group allocation.

Intervention – the intervention is a nasal saline solution which will be used for a minimum of 4 times per day.

Control – patients allocated to the control group will use usual care treatments only.

Primary outcome measure is the return of wellness, indicated by the patients' assessment of the first day of wellbeing.

Secondary outcome measures include:

1. severity and duration of troublesome nasal stuffiness
2. severity and duration of troublesome cough
3. severity and duration of rhinorrhea
4. severity and duration of malaise
5. antibiotic use
6. adverse effects of treatment
7. patient compliance
8. patient satisfaction.

Data collection – The data will be collected through patient diaries. Patients will be completed on a daily basis until general wellbeing is restored or for 6 weeks, whichever occurs first. Answers will be an indicator of the patients' subjective assessment of the severity of the symptoms each day. Restoration of general wellbeing is defined as when the patient answers 'yes' to the question 'Are you well

again?'. The diary has been adapted from one used by general practice researchers in the UK.⁷

A patient enrolment form will be used to gather basic demographic information, the duration of unwellness prior to attending the GP, and the patient's belief about the effectiveness of antibiotics for treating common cold or acute rhinosinusitis.

Patients' satisfaction with their involvement in the study and, for the nasal saline group, use of the study medication, will be assessed at the time of the final follow-up phone call by asking for patient feedback.

Follow-up – All study patients will be contacted by telephone by the Research Assistant (RA) within 2-3 days of recruitment to ensure understanding and willingness to comply with the study protocol. The RA will contact the patients again 7-9 days after recruitment to determine if symptoms have resolved or whether the patient requires another study pack. A third follow-up call will occur at about day 20, and a third study pack sent out as required. Any patients continuing the treatment / diary at the third call will receive a final follow up telephone call at 6 weeks post enrolment into the study to remind them to send back the symptom diary. The RA will remain blinded to the group to which the patient has been allocated throughout the follow-up period. Another member of staff will make up additional study packs as required.

Analysis – Data will be analysed according to the intention-to-treat principle, comparing the intervention group with the control group. Baseline characteristics and symptoms will be compared using either Student's t-test (for continuous data) or Fisher's Exact Test (for categorical data). We will analyse first day of well-being using Cox regression survival analysis, and will adjust for baseline symptom severity, and duration of illness before visiting the GP. We shall investigate the severity of illness using a symptom score collected on day 3 after enrolment. We will use a multivariate linear regression, adjusting for baseline symptom severity, and duration of illness before visiting the GP. A P-value < 0.05 will be considered statistically significant. There will be no adjustment for multiple comparisons.

Dissemination of results – The outcomes of this study will be disseminated through presentations at relevant conferences, and publication in international peer reviewed journals.

Potential Benefit of Findings

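### Antibiotic use is an undivided outcome, yet antibiotics prescribed at the recruiting visit precede allocation and are not among the listed enrolment items, which dilutes research question 2

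*Protocol*

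**What the plan says.** The order of events is explicit. In the Protocol, Methods, Participant recruitment, GPs identify patients "as they present for a consultation for treatment of the common cold or acute rhinosinusitis". Other staff then take over: "Following this consultation, the Practice Nurse (or another suitable staff member) will continue discussions with potentially interested patients", and they obtain consent. Under Randomisation and allocation to study groups, the pack that carries the allocation comes last: "Once a patient has consented to participate in the study, they will be allocated a study identifier, and will be given a study pack".

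The second item under Research question(s) asks "does isotonic nasal saline spray decrease antibiotic use compared with usual treatment". The fifth secondary outcome is "antibiotic use", with no time window and no split between courses decided at the recruiting visit and later ones.

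Under Data collection, the baseline items are described as follows: "A patient enrolment form will be used to gather basic demographic information, the duration of unwellness prior to attending the GP", together with "the patient's belief about the effectiveness of antibiotics for treating common cold or acute rhinosinusitis". Antibiotic prescribed or being taken is not in that list. No exclusion criterion removes patients who have an antibiotic. Entry requires at least 5 days of symptoms and allows up to 3 weeks, so some may already be on a course. The Background gives no rate but says that "Antibiotics are commonly prescribed in this situation".

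**The concern.** The research question is causal: does saline reduce antibiotic use? A prescription written at the recruiting consultation (the index visit) is decided before the patient is allocated. Counted as an outcome, it adds about the same number of events to each arm, and allocation had no part in the prescribing decision.

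Two things follow. The contrast between arms shrinks toward no effect. And any chance difference between arms in index-visit prescribing enters the antibiotic comparison, where it cannot be adjusted for unless the status is known.

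The pilot's stated purposes include refining trial processes and informing an appropriately powered study. A rate that mixes index-visit courses with later starts is a poor planning figure for that study.

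**Working it through.** The protocol gives no antibiotic rate, and its sample size (60, 30 per arm) has no power calculation behind it, so there is no figure to reproduce. What follows is an illustration on assumed rates.

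**Inputs**
- From the protocol: 30 per arm.
- Assumed: a share q leaves the index visit with an antibiotic and uses it whatever the allocation. Of the rest, 15% start a course later under control and 7.5% under saline, a true risk ratio (RR) of 0.50.

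**Dilution.** Any use = q + (1 − q) × new-start rate, so the risk difference shrinks by the factor (1 − q).

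| q | Control | Saline | RR | Difference |
|---|---|---|---|---|
| 0.20 | 0.20 + 0.80 × 0.15 = 0.320 | 0.20 + 0.80 × 0.075 = 0.260 | 0.81 | 6.0 points |
| 0.40 | 0.40 + 0.60 × 0.15 = 0.490 | 0.40 + 0.60 × 0.075 = 0.445 | 0.91 | 4.5 points |
| 0.60 | 0.60 + 0.40 × 0.15 = 0.660 | 0.60 + 0.40 × 0.075 = 0.630 | 0.95 | 3.0 points |

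**Chance imbalance in index-visit prescribing.** The SD of the difference between arms is √(2q(1 − q)/30): 10.3 points at q = 0.20 and 12.6 points at q = 0.40 or 0.60.

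**Precision with and without the split.**
- Any use, 30 per arm: the standard error (SE) of the difference is √[(p₁(1 − p₁) + p₂(1 − p₂))/30] = 11.7, 12.9 and 12.3 points. Effect divided by SE is 6.0/11.7 = 0.51, 4.5/12.9 = 0.35 and 3.0/12.3 = 0.24.
- New starts among patients without an index-visit antibiotic (24, 18 or 12 per arm): √[(0.15 × 0.85 + 0.075 × 0.925)/n] = 9.1, 10.5 and 12.8 points, against an effect of 7.5 points. The ratios are about 0.83, 0.72 and 0.59.

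The split improves the ratio at every q, but it stays below 1.

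**Sensitivity to the assumed rates, and the planning consequence.** With higher new-start rates (30% v 15%, RR again 0.50), a two-sided 5% test and pooled variance:

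| q | Any-use RR | Power at 30 per arm: any use / new starts | Enrolled per arm for 80% power: any use / new starts |
|---|---|---|---|
| 0.10 | 0.64 | 20% / 26% | 181 / 135 |
| 0.30 | 0.79 | 13% / 21% | 353 / 173 |
| 0.50 | 0.88 | 9% / 16% | 662 / 242 |

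The new-start enrolment figures are 121/(1 − q), rounded up, where 121 per arm is the requirement for 30% v 15%.

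**The case against.** The case on the other side has several parts.

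- **The form and the diary are not shown.** The analysis section uses baseline symptom severity, which is not among the listed form items either, so the list may not be the whole baseline dataset. The diary is daily, the first one is in the pack, and it was adapted from one used in a trial of antibiotic prescribing strategies. It may date antibiotic use. A reader might infer that antibiotic status at entry is not recorded, or that the courses can never be separated. The protocol supports only that the item is not listed and that no such use of the diary is planned. Even a dated diary could leave an index-visit prescription filled some days later looking like a new start.
- **The outcome is use, not prescribing.** A reader might infer that saline could not have prevented any index-visit course. A prescription held but not filled, or a course cut short, can still respond to allocation. That the prescribing decision falls in the index consultation is itself an inference, though a direct one.
- **No systematic bias.** A decision made before allocation is balanced in expectation, and an unadjusted SE already reflects chance imbalance. This stands in full.
- **Noise exceeds the effect in any case.** It would be tempting to blame this flaw because the imbalance SD is larger than the diluted effect. The working shows that noise still exceeds the effect after the split, because 30 per arm is small.
- **Definitions may sit in an SAP.** The time window and covariates for a secondary outcome are commonly set there, so their absence is not the point. An SAP cannot, however, recover a baseline item that was never collected.

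**Conclusion.** The point holds in a limited form. Followed as written, the plan compares undivided antibiotic use between arms when part of it was decided before allocation, and it lists no baseline item that would identify that part. The harm is dilution and unadjustable chance imbalance, not bias.

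On the assumed 15% v 7.5%, a true RR of 0.50 appears as 0.81 to 0.95 for index-visit prescribing of 20% to 60%. These figures rest on assumed rates and on index-visit courses being unaffected by allocation; if allocation changes whether those prescriptions are used, the dilution could be smaller. A diary that records start dates and the source of the prescription would largely remove the problem.

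The outcome is secondary in a 60-patient pilot that cannot settle research question 2 either way. The change is worth making because it gives an interpretable estimate and a new-start rate on which the full trial can be planned.

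**What to change.** 1. Add two yes/no items to the enrolment form, completed before the pack is handed over: whether an antibiotic is currently being taken, and whether one was prescribed at this visit.
2. Make the main antibiotic outcome a course newly started after randomisation that does not come from an index-visit prescription.
3. Report use of index-visit prescriptions separately by arm, so that any effect of allocation on filling or completing them stays visible.
4. Adjust or stratify any overall antibiotic-use comparison by index-visit antibiotic status. That status is fixed before allocation, so conditioning on it keeps the randomised comparison intact.

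The cost is two form items, a revised outcome definition and fewer events to count. At q = 0.40 and a 15% new-start rate, the control arm would expect 30 × 0.49 = 14.7 users, of whom 30 × 0.40 = 12 hold index-visit courses and only 18 × 0.15 = 2.7 are new starts. Recruitment and treatment do not change.

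### A single stated block size of ten, not said to be withheld from recruiters, makes late assignments predictable if earlier ones become known at a practice

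*Protocol*

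**What the plan says.** Protocol, Methods, Randomisation and allocation to study groups: "Randomising will be done at the Discipline of General Practice", using "computer generated random sequences in blocks of ten patients". No other block size is given, and nothing says that the size is kept from recruiters. "A set of sealed, opaque, sequentially numbered study packs will be delivered to each participating general practice". Hand-over comes after consent: "Once a patient has consented to participate in the study, they will be allocated a study identifier, and will be given a study pack". Control packs hold vapour drops of a size comparable to the spray. The stated purpose is that packs look alike and that practice staff and patients stay blinded to the group.

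Methods, Research Design: "Research Design – randomised controlled open label trial". The last paragraph of the Background also calls the trial open label.

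Methods, Participant recruitment: "Participating GPs will opportunistically identify potentially eligible patients as they present for a consultation". The GP also gauges interest and determines eligibility; a practice nurse or other staff member then takes consent.

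Methods, Recruitment of participating GPs: "there is a core group of GPs & associated general practices who have been involved in the development of this project". Three core practices are named and further GPs are expected.

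**The concern.** A sealed pack hides its own contents. It does not hide what can be inferred from earlier packs. In a balanced block of ten, once five allocations to one arm are known, every remaining pack in that block belongs to the other arm. The inference needs three things: the block size, where the block starts, and most of the earlier allocations.

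The core GPs may know the first. The pack numbers at the practice could supply the second, if blocks run within practice. The third could leak because a spray and a pack of drops are plainly different once the pack is opened, and a patient may mention which one was inside. The similar packaging can therefore protect blinding only until opening.

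At stake is selection at the moment when the GP decides whom to approach, which is before consent and before the pack changes hands. The primary outcome is the patient's own report of being well again. The Cox model in the Analysis section adjusts for baseline symptom severity and for prior duration of illness. Selection on anything else, such as a patient's wish for a spray, would not be removed. Recruitment rate is also a feasibility result of this pilot, and a larger trial may inherit the procedure.

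**Working it through.** **Inputs.** Block size 10 (Randomisation section). Sample size "60 participants, 30 in each group", so a complete block is taken as 5:5. Consistency check: 60/10 = 6 blocks, and 6 × 5 = 30 per arm, which agrees with the stated split. The protocol gives no figure for predictability to reproduce.

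**Assumptions, not stated in the protocol.** Blocks run within practice; the guesser knows the block size and the block boundaries; a share q of earlier allocations is known, each independently.

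**1. Certain assignments in a complete block, full knowledge (q = 1).** Position i is certain if the first i − 1 packs already contain all five of one arm. The probability is 2 × C(5, i−6) / C(10, i−1):

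- 6th: 2 × 1/252 = 0.8%
- 7th: 2 × 5/210 = 4.8%
- 8th: 2 × 10/120 = 16.7%
- 9th: 2 × 10/45 = 44.4%
- 10th: 2 × 5/10 = 100%

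The sum is 1.67 per block, or 16.7%. It equals 2m/(m+1) with m = 5, that is 10/6. Over six complete blocks, 6 × 1.67 = 10.

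**2. Best-guess accuracy, full knowledge (Blackwell–Hodges).** 5 + 2⁹/C(10,5) − 0.5 = 5 + 512/252 − 0.5 = 6.53 of 10, or 65.3%, against 50% by chance.

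**3. Partial knowledge, complete blocks.** Certainty requires that all five allocations of the exhausted arm are known, so the expected number is 1.67 × q⁵. Best-guess accuracy is from simulation.

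| q | certain per block | share certain | best guess correct |
|---|---|---|---|
| 1 | 1.67 | 16.7% | 65.3% |
| 0.75 | 1.67 × 0.237 = 0.40 | 4.0% | about 60% |
| 0.50 | 1.67 × 0.031 = 0.05 | 0.5% | 56.8% |
| 0.25 | 1.67 × 0.001 = 0.002 | 0.02% | 54.0% |
| 0 | 0 | 0% | 50% |

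**4. Incomplete blocks.** Certainty sits at the end of a block. A practice that stops at eight patients yields 0.008 + 0.048 + 0.167 = 0.22 certain assignments, not 1.67. The number of practices is not given, so a range is shown. Each of 60 patients is placed at random, with equal probability, in one of K practices. The full-knowledge counts come from summing step 1 over the binomial distribution of practice size; the other columns multiply them by q⁵.

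| K | q = 1 | q = 0.75 | q = 0.50 |
|---|---|---|---|
| 3 | 8.1 | 1.9 | 0.25 |
| 6 | 6.3 | 1.5 | 0.20 |
| 10 | 2.0 | 0.5 | 0.06 |

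**5. Effect of undisclosed, varying sizes (simulated, full knowledge).** The guesser knows the set of possible sizes and every earlier allocation, but not the size of the current block.

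| scheme | certain | over 80% predictable | best guess correct |
|---|---|---|---|
| fixed 10 | 16.7% | about 17% | 65.3% |
| random 6, 8, 10, 12, 14 | 0.1–0.6% | 3–6% | 62–64% |
| random 6, 8, 10, 12 | 1.1% | not computed | 64.4% |

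Varying small blocks do worse on guessing: sizes 4, 6 and 8 give 2.5% certain but 67.2% correct.

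**The case against.** The protocol has real safeguards. The list is generated centrally, packs are sealed, opaque, numbered and alike, hand-over follows consent, and staff are meant to stay blinded. Nothing says that a pack is opened at the practice. Scheduled follow-up is by telephone, by a research assistant who stays blinded, and another staff member makes up further packs. No return visit to the practice is planned. Leakage would have to come through unscheduled contact, someone would have to keep count, and that knowledge may be split between the GP who approaches and the nurse who consents. Ten is also less predictable than any smaller fixed block.

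Most of this stands, and it limits the point. A reader might infer that recruiters can work out the next allocation before approaching a patient, or that about 10 of 60 assignments are exposed. The protocol does not support either reading. It does not state that recruiters know the block size, involvement in development is stated for the core group only, and blocking within practice is an inference from the pack sets. The figure of 10 needs complete leakage and six complete blocks.

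What the safeguards do not cover is information from packs already opened. Blinding of the patient cannot last beyond opening, and no section stops a patient's account from reaching the person who selects the next one. Handing over after consent does not help either, because selection would act earlier.

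**Conclusion.** The point holds as a conditional weakness of minor severity. One fixed block size is written into the protocol with no statement that it is concealed, in an open-label trial whose core GPs may know it and who choose whom to approach. Predictability follows only if earlier allocations reach the practice and blocks run within practice.

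The plausible size runs from almost nothing, at half or fewer of the earlier allocations known, to one or two patients in 60 at 75% known over three or six practices, and to about 8, 6 or 2 patients at full knowledge over 3, 6 or 10 practices. No resulting bias in the primary outcome, and no effect on the recruitment rate, has been estimated. The documents do not show that allocation concealment fails.

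**What to change.** Under Randomisation and allocation to study groups:

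- Replace the fixed block of ten with permuted blocks of randomly varying size, for example 6 to 14.
- State that the sizes are held centrally at the Discipline of General Practice by someone who does not recruit, and that they appear in no version given to recruiting GPs or practice staff, including those who helped develop the study.
- State whether the sequence is blocked within practice.
- Reconcile the open-label description with the statement that staff and patients stay blinded, by saying who is unaware of the group and until when (for instance, until the pack is opened).

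The cost is a few sentences and a new run of the list before packs are made up, with no extra patients or staff. The downside is slightly more arm imbalance when a practice stops mid-block. Fixed blocks of ten already allow this: with 60 patients over six practices, the simulated SD of the arm difference is about 3 patients.

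The gain should not be oversold. It lies almost entirely in removing certain or near-certain assignments under heavy leakage. Overall guess accuracy barely changes, and no benefit has been calculated under partial leakage.

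### The study packs are matched on size and look only, which does not by itself hide the next allocation from practice staff who may handle the packs and who obtain consent.

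*Protocol*

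**What the plan says.** All of this is in the Protocol, under Methods.

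- **Concealment device** (Randomisation and allocation to study groups): "A set of sealed, opaque, sequentially numbered study packs will be delivered to each participating general practice". The sequence is computer generated away from the practices, in blocks of ten.
- **Spray pack** (same section): the first fortnight's diary and "sufficient study medication for a fortnight". The product is a liquid: "the intervention is a nasal saline solution which will be used for a minimum of 4 times per day".
- **Control pack** (same section): "3 packs of Vicks Vapor Drops or similar, of comparable size to the nasal saline spray".
- **What the matching is said to achieve** (same section): it "will ensure that all study packs look similar such that practice staff and patients remain blinded to group allocation".
- **Order of events** (same section): "Once a patient has consented to participate in the study, they will be allocated a study identifier, and will be given a study pack".
- **Who takes consent** (Participant recruitment): after the GP has raised the study, "the Practice Nurse (or another suitable staff member) will continue discussions with potentially interested patients, answer their questions, and obtain informed consent".

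The Research Design entry describes the trial as open label, so the pack can hide the allocation only until it is opened.

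**The concern.** In an open-label trial, the sealed pack is what keeps the next allocation unknown until the patient has been entered. The protocol treats similar appearance as sufficient for that, but the two packs hold different kinds of product. Sealing and opacity block sight. They do not equalise weight, or what is heard and felt when a pack is lifted or tilted. Because packs are numbered in sequence and are at the practice, staff know which one comes next.

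This is a different route from guessing the end of a block of ten. That needs knowledge of earlier allocations. Recognising a pack by handling it does not, and varying the block size would not prevent it.

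If staff could tell the next pack, they could defer or steer particular patients, for example those with worse symptoms or those hoping for the spray. That selection happens before allocation takes effect, so analysis by intention to treat cannot undo it. Covariate adjustment removes only the part that the covariates capture. The primary outcome is the patient's own report of being well again.

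**Working it through.** **Reading the text.** The protocol has no figure to reproduce here, so the first step is to set the statements side by side.

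1. Matching is stated on size and look. Weight, sound, movement and feel are not mentioned in any section.
2. One pack holds a fortnight's liquid and the other holds three packs of drops. The contents differ in kind, so equal weight and handling cannot be presumed.
3. The packs go to the practice, and staff of that practice take consent. Who stores the packs is not stated.
4. The order is consent, then identifier, then pack. The text does not say that the identifier is the pack number, or that a number is recorded before a pack is touched. The next pack is already on site while consent is being discussed.

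The stated matching rule therefore does not deliver the assurance that the protocol draws from it. Whether packs could in fact be told apart is not known.

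**How much it could matter.** The only input from the documents is 30 patients per arm (Sample Size). Everything else is an assumption:

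- Staff judge a prognostic score that is standard normal, with high values meaning worse prognosis.
- When the next pack is control, a patient with a score above the median is deferred with probability q. The spray arm is unselected.
- The score correlates r with the outcome.
- The planned covariates remove a fraction v of the score variance.
- A two-arm comparison of a normal outcome stands in for the planned models.

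Formulas:

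- Difference between arms in the score: d = √(2/π) × q/(2 − q) = 0.798 × q/(2 − q).
- Difference in the outcome, in residual SDs: e = r × d × (1 − v)/√(1 − r²v).
- Shift of the test statistic: s = e × √(30/2) = e × 3.873.
- Type I error: P(|Z + s| > 1.96).

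Example with q = 20%, r = 1, v = 0: d = 0.798 × 0.2/1.8 = 0.089; s = 0.0887 × 3.873 = 0.343; type I error = P(Z > 1.617) + P(Z < −2.303) = 0.053 + 0.011 = 6.4%.

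Example with q = 50%, r = 0.5, v = 0.5: d = 0.798 × 0.5/1.5 = 0.266; e = 0.5 × 0.266 × 0.5/√0.875 = 0.071; s = 0.275; type I error = 5.9%.

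| q | d (SD) | r = 1, unadjusted | r = 0.5, unadjusted | r = 0.5, v = 0.5 |
|---|---|---|---|---|
| 10% | 0.04 | 5.3% | 5.1% | 5.0% |
| 20% | 0.09 | 6.4% | 5.3% | 5.1% |
| 30% | 0.14 | 8.5% | 5.9% | 5.2% |
| 50% | 0.27 | 17.8% | 8.1% | 5.9% |

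To fill 30 control places, staff would have to defer 30/(1 − q/2) − 30 patients: about 3 at q = 20% and 10 at q = 50%.

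**The case against.** The case on the other side has real weight.

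- **The device is a standard one.** Packs are sealed, opaque and sequentially numbered, the sequence is made off site, a size-matched item is added to the control pack, and consent comes before the pack. These safeguards stand. They leave open what can be learned by handling a pack, and the missing link between identifier and pack number.
- **The physical premise is partly unknown.** The documents give no weights, padding or storage arrangements, and do not say that the person taking consent holds the packs. A reader might infer that every pack can be recognised, or that concealment has failed. The documents do not support either, and only the possibility remains.
- **The analysis already adjusts.** The Analysis section adjusts the Cox model and the linear regression for baseline symptom severity and for duration of illness before the GP visit. Steering by visible symptoms would be partly captured, so the unadjusted columns describe a test that is not planned for these outcomes.
- **Perfect prediction is unrealistic.** The r = 1 column assumes that staff can foresee recovery exactly. A reader might take 17.8% as the expected error rate, but it is a bound. With r = 0.5 and q of 20% or less, the inflation is negligible.
- **This is a 60-patient pilot and pack make-up is a detail.** That limits the consequence. However, the Aims include refining the trial's processes, and the protocol makes a positive claim about what the matching achieves. The claim can be corrected now, before a larger trial inherits the packs.

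**Conclusion.** The point holds as a cheap improvement to make. Similar size and look do not ensure that practice staff stay unaware of the next allocation when one pack holds liquid and the other holds drops, and no pack number is stated to be committed before handling. The breach is possible, not shown, and its size is unknown.

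Within the one-sided deferral model, the upper bound for an unadjusted 5% test is 6.4% at q = 20% and 17.8% at q = 50%. With r = 0.5 it is about 5.3% and 8.1%, and about 5.1% and 5.9% if the covariates remove half of the score variance. The values of q, r and v are assumptions, because the documents supply none of them. The bias could favour either arm, depending on whom staff chose to defer.

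**What to change.** In the Protocol, Randomisation and allocation to study groups:

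1. Require packs to be matched on weight, and on sound and movement when handled, as well as on look. Padding or wrapping the contents would do this.
2. Make the pack number the study identifier.
3. Require that number to be logged against the patient after consent and before any pack is picked up.

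Optionally, have someone outside the trial try to sort a few finished packs by hand before release.

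The cost is packing material, slightly more work in making up packs, and one log line per patient. No extra patients or staff are needed, and the contents of the packs and the planned analysis stay as they are.
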